**CONFIDENTIAL**

## Statement of Compliance

This study will be conducted in accordance with the Code of Federal Regulations on the Protection of Human Subjects (45 CFR Part 46), 21 CFR Parts 50, 56, 312, and 812 as applicable, any other applicable US government research regulations, and institutional research policies and procedures. The International Conference on Harmonisation (“ICH”) Guideline for Good Clinical Practice (“GCP”) (sometimes referred to as “ICH-GCP” or “E6”) will be applied only to the extent that it is compatible with FDA and DHHS regulations. The Principal Investigator will assure that no deviation from, or changes to the protocol will take place without prior agreement from the sponsor and documented approval from the Institutional Review Board (IRB), except where necessary to eliminate an immediate hazard(s) to the trial participants. All personnel involved in the conduct of this study have completed Human Subjects Protection Training.

CONFIDENTIAL

This material is the property of the NYU School of Medicine and Langone Medical Center. Do not disclose or use except as authorized in writing by the study sponsor

### List of Abbreviations

ASA	American Society of Anesthesiologist Score
BMI	Body Mass Index
DOS	Day of surgery
VAS	Visual analog scale
AE	Adverse event
SAE	Serious adverse event
IV	Intravenous
ITT	Intention-to-treat
PACU	Post-Anesthesia Care Unit
PEC	Pectoralis nerve block
PO	Taken orally
PRN	Taken as needed
PROMIS	Patient Reported Outcomes Measurement Information System
CI	Confidence interval
SD	Standard deviation; a parameter that characterizes a population distribution
SE	Standard error
ANOVA	Analysis of variance; a linear model
NSAID	Non-steroidal anti-inflammatory drug

### CONFIDENTIAL

## Protocol Summary

Title	Pecs II Block versus Surgeon Infiltration for Open Subpectoral Biceps Tenodesis
Brief Summary	A phase IV, randomized, single-blind, single-center study measuring the effects of Pecs II block with 0.25% bupivacaine versus surgeon infiltration with 0.25% bupivacaine on postoperative pain control and opioid utilization in participants who undergo open subpectoral tenodesis.
Phase	Clinical study phase IV
Objectives	To determine if Pecs II block is superior to surgical infiltration in reduction of axillary pain after open subpectoral bicep tenodesis, especially in terms of duration.
Methodology	Phase IV, randomized, single-blind, single-center study
Endpoint	
Primary Endpoint: Opioid utilization for the first 24 hours after surgery, including during surgery, calculated as oxycodone equivalent.
 
Secondary Endpoints: Patient reported VAS scores in PACU Patient reported VAS scores on POD 1 and POD 3 Reaction to surgical subpectoral incision (signs include patient movement, tachycardia, etc.) Skin assessment of sensation in PACU (axilla, distal to surgical dressing)

Study Duration	The study will continue until 80 subjects are enrolled per arm, to allow for potential dropout and increased power.
Participant Duration	Each participant will be enrolled on DOS and complete their final follow up on postoperative day three.
Duration of IP administration	Once during surgery
Population	80 patients per study arm scheduled for open biceps tenodesis
Study Sites	NYU Langone Orthopedic Hospital and NYU Ambulatory Surgery Center at 38 th street
Number of participants	160
Description of Study Agent/Procedure	Patients in both groups will receive an interscalene nerve block with 20 mL 0.5% bupivacaine. Subjects in the Pecs II block group will receive a Pecs II fascial plane block with 20 mL 0.25% bupivacaine. The Surgical infiltration group patients will receive local infiltration of 0.25% bupivacaine by the surgeon, up to 15 mL.
Reference Therapy	Reference is Interscalene block with 0.5% bupivacaine and surgical infiltration with bupivacaine 0.25%
Key Procedures	Interscalene block with 0.5% bupivacaine, Pecs II block with 0.25% bupivacaine, local surgical infiltration with 0.25% bupivacaine
Statistical Analysis	Continuous and categorical baseline characteristics will be compared using Hedges standardized difference. Outcomes will be assessed using an intention-to-treat (ITT) methodology. Normally distributed data will be compared using t tests while non-normally distributed continuous outcomes will be assessed using the Mann-Whitney U test.

## **1 Background and Specific Aims**

Biceps tendinopathy can range from inflammatory to degenerative pathology and can often contribute to anterior shoulder pain. This pain is generally located at the anteromedial aspect of the shoulder in the area of the intertubercular groove. Surgical treatment by biceps tenodesis can help increase strength and decrease pain in patients that have failed non-operative management. Although there are many variations to the surgical approach, one approach that has been shown effective is the open subpectoral biceps tenodesis.

For arthroscopic and open shoulder surgeries, assuming there are no contra-indications, anesthesiologists at our institution most often perform interscalene brachial plexus blocks along with IV sedation. The brachial plexus provides innervation to most of the shoulder joint and adjacent soft tissue. Nerves that require blockade to achieve effective analgesia include the subscapular, axillary, lateral pectoral, and suprascapular nerves. These nerves are anesthetized with the interscalene brachial plexus block which targets the C5-6 nerve roots and spares the inferior trunk of the brachial plexus. When an open subpectoral biceps tenodesis is being performed, either alone or with shoulder arthroscopy, a vertical incision is made along the anteromedial aspect of the arm centered over the pectoralis major tendon. Unfortunately, this area of the upper arm is not anesthetized by the interscalene brachial plexus block.

The anteromedial aspect of the upper arm is typically innervated by the medial brachial cutaneous nerve and the medial pectoral nerve, which arise from the inferior trunk of the brachial plexus, along with the intercostobrachial nerve, which originates from the T2 nerve root. In order to anesthetize this area, one can consider utilizing the Pecs II block. The Pectoralis nerve blocks (Pecs) were initially intended for breast surgeries; however, they have also become a popular substitute for paravertebral blocks and thoracic epidurals following thoracic and abdominal wall surgeries. The Pecs I block consists of an injection of local anesthesia between the pectoralis major and minor

### CONFIDENTIAL

This material is the property of the NYU School of Medicine and Langone Medical Center. Do not disclose or use except as authorized in writing by the study sponsor

muscles. This is intended to block the medial and lateral pectoral nerves. The Pecs II block consists of an additional fascial injection between the pectoralis minor muscle and the serratus anterior muscle, and anesthetizes the upper intercostal nerves. Reynolds previously demonstrated that the Pecs II block is beneficial in decreasing postoperative axillary pain during an open biceps tenodesis compared to no block. However, patients in that study received general anesthesia for the surgery. The alternative to performing a Pecs II block would be surgical infiltration of local anesthesia at and around the incision site. Prior to this study, our institution relied heavily on this alternative to adequately provide analgesia to the anteromedial upper arm and decrease postoperative axillary pain.

To date, there are few studies on surgical infiltration for open biceps tenodesis. Based on the success of the Pecs II block for open bicep tenodesis demonstrated by Reynolds, we propose this randomized controlled study comparing a Pecs II block versus surgical infiltration for this procedure. We hope to elucidate which technique will provide better pain control after open subpectoral bicep tenodesis surgery.

### 1.1 Specific Aims

This study will aim to compare Pecs II block versus surgical infiltration for axillary pain in patients undergoing arthroscopic shoulder surgery with an open subpectoral bicep tenodesis.

**AIM 1:** To determine if Pecs II block is superior to surgical infiltration in reduction of axillary pain after open subpectoral bicep tenodesis, especially in terms of duration.

### 1.2 Statistical Hypothesis

We hypothesize that patients who receive a Pecs II block will have lower postoperative opioid consumption over the first 24 hours (measured in oxycodone equivalents) compared to those who receive surgical infiltration of local anesthetic. Furthermore, the Pecs II block patient group will have reduced adverse effects associated with opioids such as constipation, nausea, pruritis ileus. Failing to reject the null would signify that the Pecs II block has no clinically relevant difference on post-operative opioid consumption outcomes in Open Subpectoral Biceps Tenodesis as compared to surgical infiltration of local anesthetic.

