#### Secondary Endpoints:

1. Patient reported NRS scores in PACU and at 24 hours
2. Patient Reported NRS scores on POD 1 and POD 3
3. Reaction to surgical subpectoral incision (signs include patient movement, tachycardia, etc.)
4. Skin assessment of sensation in PACU (axilla, distal to surgical dressing)

Normally distributed data such as the primary outcome variable will be compared using the two-sample t-test. In the case that the data are not normally distributed, the Wilcoxon rank-sum test will be used instead. Categorical variable will be compared using the Chi-Squares unless other tests such as the Fisher's exact test are more appropriate.

All endpoints will be evaluated as fits the data set with graphical figures such as scatter plots, box-and-whisker plots, and frequency histograms to visualize the distribution of these outcomes and their relationships to covariates and treatment assignment. When appropriate descriptive graphical and tabular methods will also be estimated and presented in a graphical figure.

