### 6.3 Sample Size

80 subjects will be enrolled

Based on published reports (Reynolds et al) and our clinical experience, we estimate that patients in the Pecs group will use only 25 mg of oxycodone-equivalent, while patients receiving the infiltration will use 32 mg. Using a 2-sided, 2-sample t test, an  $\alpha$  value of 0.05 and assuming a common SD of 13, a power analysis revealed that 72 subjects were needed per group for a power of 0.90. We chose to enroll 80 subjects per arm to allow for potential dropout and an increased power.

CONFIDENTIAL

This material is the property of the NYU School of Medicine and Langone Medical Center. Do not disclose or use except as authorized in writing by the study sponsor

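### Section 1.2 reads a non-significant superiority test as proof of no clinically relevant difference, but the plan sets no margin, equivalence test or confidence interval to support that.

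*Combined protocol and SAP*

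**What the plan says.** Section 1.2 first states a directional hypothesis: opioid consumption over the first 24 hours, in oxycodone equivalents, will be lower with Pecs II than with surgeon infiltration. It then gives a rule for a null result: "Failing to reject the null would signify that the Pecs II block has no clinically relevant difference on post-operative opioid consumption outcomes". Section 1.1 is also framed as superiority ("To determine if Pecs II block is superior to surgical infiltration in reduction of axillary pain"), although that aim concerns pain. The superiority framing of the opioid endpoint rests on Section 1.2.

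Section 6.3 sizes the trial as a superiority comparison: "Using a 2-sided, 2-sample t test", alpha 0.05. The planning values are "we estimate that patients in the Pecs group will use only 25 mg of oxycodone-equivalent, while patients receiving the infiltration will use 32 mg" and "assuming a common SD of 13, a power analysis revealed that 72 subjects were needed per group for a power of 0.90"; 80 per arm are to be enrolled. The 7 mg difference is presented as an expectation, not as the smallest difference that matters.

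For the analysis, the Protocol Summary says "Normally distributed data will be compared using t tests while non-normally distributed continuous outcomes will be assessed using the Mann-Whitney U test", Section 6.1 repeats this, and Section 6.2 adds "In the case that the data are not normally distributed, the Wilcoxon rank-sum test will be used instead". No estimate or interval for the between-arm difference is named. The term "Confidence interval" occurs only in the List of Abbreviations.

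**The concern.** Failing to reject a null hypothesis of no difference means that the data are compatible with zero. It does not mean that they are incompatible with a difference that matters. To conclude the latter, one must say how large a difference matters and show that the data exclude it. The plan does neither.

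If Section 1.2 is followed, a result that is merely inconclusive would be reported as showing that the two techniques do not differ in any relevant way, even when the data still allow the whole effect on which the trial was sized. The sentence leaves a non-significant primary result no inconclusive category.

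**Working it through.** **Inputs.** From Section 6.3: means 25 and 32 mg (difference 7 mg), common SD 13 mg, two-sided alpha 0.05, 72 per group for power 0.90, 80 per arm enrolled. Section 6.1 excludes patients whose primary outcome cannot be ascertained, so fewer than 80 per arm may be analysed; results are given for 80 and 72. All figures assume normal data and the t test, so they do not describe the rank-sum branch. The 7 mg is used as a reference point only, because the documents give no relevance threshold.

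**The plan's own figure.** For a difference of 7 mg, SD 13 and power 0.90, the normal approximation gives 73 per group and the noncentral t gives 73.45, so 74. Power at 72 per group is 0.894 (t) or 0.898 (normal). The stated 72 reproduces to within two patients; the sample size is not at issue. Power at 80 per arm is 0.923.

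**Width of the interval.** Half-width = t(0.975, 2n-2) × SD × √(2/n).
- 80 per arm: 1.975 × 13 × √(2/80) = 1.975 × 2.055 = 4.06 mg.
- 72 per arm: 1.977 × 13 × √(2/72) = 1.977 × 2.167 = 4.28 mg.

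**What a non-significant result can still contain.** A result is non-significant when the observed difference is smaller than the half-width, so the upper limit can approach twice the half-width: 8.1 mg at 80 per arm, 8.6 mg at 72. The interval still includes 7 mg when the observed advantage is at least 7 minus the half-width:
- 80 per arm: 7 - 4.06 = 2.94, so observed advantages of about 2.9 to 4.1 mg.
- 72 per arm: 7 - 4.28 = 2.72, so about 2.7 to 4.3 mg.

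Examples at 80 per arm with an observed SD of 13:

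| Observed advantage | p | 95% CI |
|---|---|---|
| 2 mg | 0.33 | -2.1 to 6.1 mg |
| 3 mg | 0.15 | -1.1 to 7.1 mg |
| 4 mg | 0.053 | -0.1 to 8.1 mg |

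Section 1.2 gives all three the same reading.

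The observed SD will itself vary. If the true SD is 13, its 95% range is 13 × √(χ²(p, 2n-2)/(2n-2)), which is 11.6 to 14.4 at 80 per arm. Over that range the reach of a non-significant interval is 7.2 to 9.0 mg (7.6 to 9.6 mg at 72 per arm).

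**How often it would happen.** The first column of results is from the noncentral t. The second is from simulation with the SD estimated in each trial. The true difference is 7 mg throughout.

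| Per arm, true SD | Non-significant | Non-significant and CI still includes 7 mg |
|---|---|---|
| 80, SD 13 | 7.7% | 5.2% |
| 72, SD 13 | 10.6% | 8.1% |
| 80, SD 10 (assumed) | 0.7% | under 0.01% |
| 80, SD 16 (assumed) | 21.5% | about 19% |

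The 7.7% is the ordinary type II error. The part specific to Section 1.2 is the 5.2%, where reading the interval would have prevented the claim. In the remaining 7.7 - 5.2 = 2.5% the interval wrongly excludes 7 mg, and either reading goes astray.

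**Smaller true differences.** At 80 per arm and SD 13, the result is non-significant in 17% of trials if the true difference is 6 mg, 32% if 5 mg and 51% if 4 mg. The documents do not say whether such differences are clinically relevant.

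**The case against.** The best defence is power. At 80 per arm the trial has about 92% power for 7 mg, so a null result is real evidence against a difference of that size. Section 5.2 also allows that the study could be inconclusive, which suggests the authors recognise that outcome. The sentence sits in the hypothesis section and the analysis sections do not repeat it, so it could be put right at reporting with no loss of data.

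Part of this stands. The effect is confined to how a null result is read, and under the plan's own assumptions the avoidable error is about one trial in twenty. With an SD of 10, reading the interval would change almost nothing at 7 mg.

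It does not rescue the sentence. The 7 mg is never declared to be the smallest relevant difference, and the claim is about any clinically relevant difference. Power is a pre-trial property that depends on the assumed SD and on retention; what the data exclude is shown by the interval, which is not planned. Section 5.2 does not tie an inconclusive study to any test result, so it does not correct Section 1.2.

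**Conclusion.** The concern holds. The rule in Section 1.2 is wrong as written, because nothing in the Protocol Summary or Section 6 supplies what its conclusion needs. With SD 13, a non-significant 95% interval can reach about 8.1 mg at 80 per arm or 8.6 mg at 72. If the true difference is 7 mg, the claim would be made while the interval still includes 7 mg in 5.2% or 8.1% of trials respectively, and in about 19% at 80 per arm if the SD were 16. These figures rest on normal data, the t test and 7 mg as an illustrative reference. The data, the superiority test, alpha and sample size are not affected. It should be fixed, and before outcomes are compared by arm.

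**What to change.** 1. **Section 1.2.** Replace the sentence with: *Failure to reject the null will be reported as no difference demonstrated; by itself it does not show absence of a clinically relevant difference.*
2. **Section 6.2.** Add: *The mean difference in oxycodone equivalents (infiltration minus Pecs II) will be reported with its 95% confidence interval, and a null result will be interpreted by the differences that the interval excludes. If the rank-sum test is used, its p-value decides significance, the interval describes size, and any disagreement between the two will be reported.* On that branch, a Hodges-Lehmann estimate with its interval could be added, since it corresponds more closely to the rank test than a mean difference does.
3. **Optional.** Claim no clinically relevant difference only if the whole interval lies within a margin that the sponsor justifies on clinical grounds and fixes before outcomes are compared by arm, whether or not the test is significant. The 7 mg planning difference should not become the margin by default. Without a fixed margin, no such claim is made.

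**Cost.** Steps 1 and 2 take a few sentences and no extra data or patients. The price is that fewer null results can be described as showing no difference.

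Step 3 may be out of reach at this size. With an observed SD of 13, a margin below about 4.1 mg (80 per arm) or 4.3 mg (72) cannot be met with a 95% interval even if the observed difference is zero. If the true difference is zero and the SD is 13, the whole 95% interval lies within 5, 6 or 7 mg in 35%, 65% or 85% of trials at 80 per arm (26%, 57%, 79% at 72). The usual equivalence test, two one-sided tests at 0.05, corresponds to a 90% interval and is less demanding: about 56%, 79% and 92% at 80 per arm, with a floor of about 3.4 mg. The sponsor should state which level applies. These margins are illustrations only.

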### 1.3 Objectives and Purpose

The goal of this study is to compare the postoperative pain control using a Pecs II block with 0.25% bupivacaine to the standard of care of local surgeon infiltration with 0.25% bupivacaine following open subpectoral biceps tenodesis, particularly in terms of duration of pain control and adjunctive postoperative analgesic consumption. The primary objective will be to compare opioid utilization between the two arms within the first 24 hours after surgery, including intraoperatively, as measured by oxycodone equivalents. Our secondary objectives are measuring patient reported pain scores in PACU and at 24 hours, reaction to surgical incision, and skin assessment of sensation in the PACU.

## 2 Study Design and Endpoints

Arm 1: Experimental	Arm 2: Control
Sample Size: 80	Sample Size:80
Medication: 20ml 0.5% bupivacaine for ISB + 20ml 0.25 % bupivacaine for Pecs II	Medication: 20ml 0.5% bupivacaine for ISB + 15ml 0.25% bupivacaine for surgical infiltration

CONFIDENTIAL

This material is the property of the NYU School of Medicine and Langone Medical Center. Do not disclose or use except as authorized in writing by the study sponsor

--	--

## 2.1 Description of Study Design

### RECRUITMENT PHASE/CONSENTING PHASE:

Surgeons will inform eligible patients of the study during their pre-surgical visit in their office. If the patient is agreeable, a member of the research team will provide further details and ask the patient to participate on day of surgery. Patients will be made acquainted with the study before DOS during pre-surgical appointments. On DOS when they arrive 1.5/2 hours before surgery we (study team members) will consent them and provide ample time to discuss and review any questions or concerns they may have.

### BASELINE ASSESSMENTS:

Subjects will complete a baseline global health and pain assessment.

### RANDOMIZATION PHASE:

Subjects scheduled to undergo open subpectoral biceps tenodesis will be randomized to either Pecs II block with bupivacaine 0.25% or subpectoral surgical skin infiltration with bupivacaine 0.25%. A randomization scheme will be created prior to start of study enrollment using the randomizer.org website to generate the assignment. Block randomization is commonly used in clinical trial design to reduce bias and achieve balance in the allocation of participants to treatment arms throughout the course of the study. Randomized block design allows us to account for variables so that observed differences are largely due to true differences between treatments and not to the variable. The greatest variable affecting the PECS study is surgical technique and it could possibly vary throughout the duration of the study. We will create blocks of four patients and in each block, two patients will be assigned to the PECS II group, and two to the infiltration group. Thus, patients in both groups will be evenly spread from the beginning to the end of the study period.

A research coordinator will place the randomization results in sealed opaque envelopes prior to recruitment. Each subject enrolled in the study will be assigned a number and the sealed envelope assigning the subject to the PECS II versus surgical infiltration arm will be opened on the day of surgery after the patient has signed consent agreeing to participate in the study.

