### **3.6 Total Number of Participants and Sites**

Recruitment will end when 160 participants have been enrolled. It is expected that there will be subjects enrolled who will be lost to follow up and be evaluated by intention-to-treat. The sites for enrollment will be the NYU Langone Orthopedic Hospital and NYU Ambulatory Surgery Center at 38th street.

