#### 6.2.1 Baseline Descriptive Statistics

The following patient data will be recorded: age, gender, height, weight, date of admission, date of discharge, laterality, surgical approach, implants used, duration of surgery, contamination, ASA, comorbidities (smoking, cardiac history, diabetes etc.), and medications. This information will be accessible in the patient's medical record.

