## 6.4 Enrollment/Randomization/Masking Procedures

We will utilize randomization.com to generate a block randomization assignments for all 160 participants. Someone that is not a stakeholder in the study will make randomization envelopes, which include the study ID number, the treatment assignment, and dosage specifics. These randomization envelopes will then be distributed to the anesthesiologist pre-operatively by the authorized researcher after informed consent is obtained.

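### Blocks of four balance the arms over time, not across surgeons or sites, and surgeon and site are neither listed data nor terms in the primary comparison

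*Combined protocol and SAP*

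**What the plan says.** The randomization paragraph of section 2.1 gives the reason for blocking: "Randomized block design allows us to account for variables so that observed differences are largely due to true differences between treatments". It then names the variable it has in mind: "The greatest variable affecting the PECS study is surgical technique and it could possibly vary throughout the duration of the study". The remedy is "We will create blocks of four patients and in each block, two patients will be assigned to the PECS II group", with the other two going to infiltration. The stated result is: "Thus, patients in both groups will be evenly spread from the beginning to the end of the study period".

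Section 6.4 adds: "We will utilize randomization.com to generate a block randomization assignments for all 160 participants". Neither section names a stratification factor. The two sections also name different list-generating websites.

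Section 3.6 and the Protocol Summary name two enrolling facilities, although the Summary also calls the study single-center. Section 2.1 refers to surgeons in the plural: "Surgeons will inform eligible patients of the study during their pre-surgical visit in their office". Their number is not given.

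The data list in section 6.2.1 reads "age, gender, height, weight, date of admission, date of discharge, laterality, surgical approach, implants used, duration of surgery", followed by contamination, ASA, comorbidities and medications. Surgeon, anesthesiologist and site are not on it. Sections 6.1 and 6.2 specify a two-sample t test, or a rank-sum test if the data are not normal. Covariates appear only in connection with plots, and none is named.

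**The concern.** A reader of 2.1 could conclude that technique has been dealt with by design. For differences between surgeons or sites it has not. A block of four taken in order of enrollment can mix surgeons and facilities, and nothing makes the split 2:2 within any of them.

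The endpoint gives operator and site ways to matter. The surgeon delivers the control and the anesthesiologist delivers the Pecs II block, both unblinded (2.1, treatment phase). The opioid total includes intraoperative use (6.2), and postoperative medication is chosen by the clinical staff caring for each patient (2.1, post-operative phase). The documents do not say that technique or opioid practice actually differs by surgeon or site. They only make it plausible.

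Two things are at stake. Variation between operators and sites stays in the error term when it could be removed. And with surgeon and site unlisted, the planned baseline comparison cannot show an imbalance in them, nor can the report show whether one surgeon's infiltration results drive the finding.

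**Working it through.** **1. The plan's own figure.** Inputs from section 6.3: means 25 and 32 mg (difference 7), SD 13, two-sided alpha 0.05, power 0.90.

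- Normal approximation: n = 2 × [13 × (1.960 + 1.282) / 7]² = 72.5, so 73 per group.
- Exact t test: 73.45, so 74 per group.

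The stated 72 reproduces to within 2 patients. At the planned 80 per arm, exact power is 0.923.

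**2. What one unstratified list does for balance.** The splits below are assumptions, because the documents give none. The simulation used 5,000 runs of 160 patients, with site or surgeon arriving in random order and 40 blocks of four. D is the arm difference in patients within one stratum.

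| Assumed strata | SD of D, blocked list | SD of D, simple randomization | Chance that some stratum is split 60:40 or worse, blocked list |
|---|---|---|---|
| 2 sites, 80 and 80 | 6.3 | 8.9 | 1.6% |
| 2 sites, 120 and 40 (D for the site of 40) | 5.5 | 6.3 | 20% |
| 4 surgeons of 40 | 5.5 | 6.4 | 53% |
| 8 surgeons of 20 | 4.1 | 4.5 | 99% |

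For surgeons, the blocked list is little better than simple randomization. Two equal sites are a mild case.

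**3. Size of a chance shift, two equal sites.** The 95th percentile of |D| is 12 patients, that is 46 against 34, or 12/80 = 15 percentage points. With an assumed site gap in mean opioid use:

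- 5 mg: 0.15 × 5 = 0.75 mg
- 7 mg: 0.15 × 7 = 1.05 mg
- 10 mg: 0.15 × 10 = 1.5 mg

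The standard error of the planned comparison is 13 × √(2/80) = 2.06 mg, so these near-extreme shifts are 0.36 to 0.73 of one standard error. They do not add to it. A gap g between two equal sites contributes variance (g/2)². For 5 mg that is 6.25/169 = 4% of the total variance, and for 10 mg it is 25/169 = 15%. Both lie inside the SD of 13 if that figure is the total SD among patients in an arm, which is how the t-test calculation uses it.

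**4. What adjustment would recover.** Residual SD = 13 × √(1 − R²), where R² is the assumed share of variance explained by surgeon and site. Power is for a difference of 7 with 80 per arm, ignoring the few degrees of freedom spent.

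| R² | Residual SD (mg) | Power |
|---|---|---|
| 0 | 13.0 | 0.923 |
| 5% | 12.7 | 0.935 |
| 10% | 12.3 | 0.946 |
| 20% | 11.6 | 0.966 |

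**The case against.** The strongest reply is that 2.1 worries about technique changing during the study and claims only that the arms are spread evenly from start to end. Blocks of four deliver that. This stands. The overreach is confined to the general statement that block design accounts for variables.

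Second, an unadjusted test in a randomized trial is valid, and power is already above target. This also stands: adjustment here is about precision and transparency.

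Third, technique is partly captured through surgical approach, implants and duration of surgery. That is true, but none of the three enters the analysis. Duration, and possibly implant choice, are fixed after the envelope is opened by a surgeon who knows the allocation, so they are poor covariates. Surgeon and site can be known before randomization. They should also be recoverable from the medical record, although the plan does not say so. The gap is therefore an omission from a list, not lost data.

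Fourth, a single list is not stated outright. It is inferred from the wording about all 160 participants and the absence of any stratum.

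A reader might infer that the comparison is biased, or that a shift of about 1 mg comes on top of the reported uncertainty. The documents support neither. Allocation is random, so the imbalance averages to zero, and the confidence interval already covers it.

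**Conclusion.** The point holds in a limited form. Enrollment-order blocks handle shared drift in technique. Nothing in the plan handles differences between surgeons or between the two sites: no stratum is named, neither factor is recorded, and neither is in the primary test. The cost is chance imbalance and lost precision, with no bias on average and no inflation of type I error.

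The size cannot be derived from the documents. The gain of roughly 1 to 4 percentage points of power rests wholly on the assumed 5% to 20% of variance explained. Imbalance is mild for two equal sites and more likely as the number of surgeons grows. The missing fields and the overbroad sentence in 2.1 do not depend on any assumed number. This is a cheap improvement worth making, not a flaw that undermines the trial.

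**What to change.** - **Section 6.2.1:** add surgeon, block anesthesiologist and site.
- **Section 6.2:** make the primary comparison a linear model with arm, site and surgeon. State in advance how low-volume surgeons are pooled, and what happens to the site term if each surgeon works at only one site. Name a counterpart for non-normal data, such as robust standard errors or a stratified rank-sum test, so that the present fallback is replaced and not simply dropped. Keep the unadjusted test as a sensitivity analysis. Finalize this before anyone sees outcome data by arm.
- **Descriptive summary:** tabulate opioid use by arm within surgeon. A main-effects model cannot show whether one surgeon's infiltration results drive the finding.
- **Section 2.1:** say that the blocks balance the arms over time only.
- **Optional, only if enrollment has not started:** separate lists by site, with varied block sizes. Fixed blocks of four within each site, with unblinded operators, would make the last assignments in a block easier to predict than on a shared list. If enrollment has begun, keep the existing list and make only the data, analysis and wording changes.

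The cost is three recorded fields and a few degrees of freedom. No extra patients are needed.
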